### 3.0 Intervention to be studied

**RESP-FIT.** The RESP-FIT program is a 6-week respiratory muscle strength training intervention adapted from previous RMST training regimens (Sapienza, Troche, Pitts & Davenport, 2011; Martin & Davenport, 2011; Hegland et al., 2016), consisting of 1) five training days/week using a combined IMST/EMST training device to which we will add Bluetooth enabled frequency and pressure intensity feedback monitoring to determine adherence and precise timing for device threshold intensification (i.e., increasing resistance training) 2) individualized, progress-based text message training reminders and prompts related to timing and intensification calibration, and 3) use of a Fitbit for remote monitoring of physical activity and hours slept at night. The training device is calibrated at 70% of each individual’s baseline PImax and PEmax. Similar to other muscle strength training programs, exercises are done at regular intervals during the week (5 breaths, 5 times a day, 5 days a week; the participant will receive graphical illustration of RESP-FIT training frequency and intensity achieved, and based on their training regimen, will be prompted and/or reinforced via SMS text messaging. Note, this feedback system allows personalized, calibrated, and efficiently timed adjustments of resistance training intensity as respiratory muscle strength improves, rather than simply increasing levels weekly. As the use of an accelerometer or remote tracking device alone may affect physical activity, a control group will receive only the Fitbit. **This study proposes to assess the initial efficacy of RMST by obtaining estimates of variability in fatigue secondary to dyspnea, using a technologically-enhanced RESP-FIT intervention.**

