## 7.0 Setting

This is not a multi-site trial. All aspects of this study will take place on-campus at MUSC or at the participant's place of residence. Informed consent will be conducted in the privacy of a patient room. The initial baseline and final study visits will occur at SCTR Nexus Research Center. All other study visits will be conducted either electronically over the tablet or by phone with the participant at their place of residence.

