### Objective Measures:

| Data Collection   | Measures   | Data sources and time points  |
|---|--|---|
| Demographics  | Age, health history, race/ethnicity, rural/urban residence, insurance  | Participant interview and medical records   |
| Clinical Characteristics                                    | FEV1/FVC
Self-reported hospitalizations/exacerbations   | Participant interview and medical records; PFT baseline and at second study visit |
| Maximal Inspiratory & Maximal Expiratory Pressure Generated | MIP and MEP recorded using a calibrated MicroRPM respiratory pressure meter, units in cm H 2 O ; a surrogate parameter for respiratory muscle weakness/strength | Collection and calibration at baseline, and at second study visit.                |
| Physical Activity: Steps                                    | # of steps taken daily (via Fitbit Alta)   | Daily   |
| Physical Activity: Patterns of Active Minutes               | # of minutes active throughout the day (via Fitbit Alta)   | Daily   |
| Sleep   | Hours of Sleep (via Fitbit Alta)   | Daily   |

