**Randomization and Training Regimen:** Following collection of pre-training baseline measures, participants will be randomly assigned 50/50 to either a Standard of Care (SOC) Control Group (n=15), or a SOC + EMST/IMST Group (n=15). Participant randomization will be stratified by gender and dyspnea grade as measured on the MMRC. Those participants assigned to the SOC control group will receive a Fitbit monitoring device, but no intervention beyond that which is typically provided to patients seen within the MUSC Clinic. Participants randomly assigned to receive SOC+EMST/IMST will receive six weeks of clinician-guided, scripted RMST. This training will be facilitated by the PI using a custom-designed and constructed EMST/IMST trainer. Non-invasive measurement of maximum expiratory and inspiratory pressures (PEmax and PImax; described previously) will be obtained in order to set pressure threshold of the EMST/RMST device. The first week of EMST/IMST training will be conducted with the device set at 75% of the average initial PEmax collected at pre-training baseline. After a nose clip is placed the participants will be taught a four-step procedure: 1) take a breath in, 2) wrap lips tightly around the EMST/IMST trainer mouthpiece, and 3) exhale quickly and forcefully until you hear the popping or whistling sound of the device valve opening, and 4) continue blowing forcefully for two seconds. Once the participant is able to do a five-breath trial, another five-breath trial will be completed with the participant allowed as much independence as appropriate. The participant will receive a text message each day reminding them to complete his or her training and "remain active today." Participants in the SOC group will receive a text message reminding them to "remain active today." The daily training session will be as follows: 1) five sets of five-breath exhalations (25 breaths total) completed each training day, 2) each exhalation within a set will be separated by approximately one minute, and 3) each five-breath training set will be separated by five minutes. A Bluetooth-enabled "use" button on the EMST/IMST device will log the times the participant has used their training device. Each participant will be provided with a diary to record five sets of five-breath training trials on five days each week. Our experience indicates that EMST/IMST takes approximately 20 minutes each day. PEmax will be reassessed weekly, by the research clinician across the six-week treatment period and readjusted to 75% of the participant's current PEmax. If no changes in PEmax are observed week to week, treatment

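### Two load-escalation rules conflict on trigger, timing and actor, so treatment fidelity, a primary analysis, has no single standard to be scored against

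*Combined protocol and SAP*

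**What the plan says.** **Rule in section 3.0 (RESP-FIT).** The trainer will be given "Bluetooth enabled frequency and pressure intensity feedback monitoring to determine adherence and precise timing for device threshold intensification", and participants will receive "individualized, progress-based text message training reminders and prompts related to timing and intensification calibration". The stated advantage is "efficiently timed adjustments of resistance training intensity as respiratory muscle strength improves, rather than simply increasing levels weekly". The starting load is 70% of baseline PImax and PEmax.

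**Rule in section 10.0 (Randomization and Training Regimen).** Week 1 is trained at 75% of the average baseline PEmax. After that, "PEmax will be reassessed weekly, by the research clinician across the six-week treatment period and readjusted to 75% of the participant's current PEmax". If PEmax has not changed from one week to the next, the load is not increased. For device logging, the paragraph says that a Bluetooth "button on the EMST/IMST device will log the times the participant has used their training device".

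**Where and when pressures are measured.** Section 7.0 places the baseline and final visits at the research center, and adds: "All other study visits will be conducted either electronically over the tablet or by phone with the participant at their place of residence". For MIP and MEP the Objective Measures table gives: "Collection and calibration at baseline, and at second study visit". The Participant Compensation paragraph puts Visit 2 at week 6. The end of the training-regimen text, however, has every dependent variable measured in all participants at baseline, week 3, week 6 and week 14.

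**Device and analysis.** The RESP-FIT Training paragraph of section 3.0 gives a pressure range of 1.5 to 20 cm H2O. Section 12.0 counts treatment fidelity and adherence among the primary analyses and PImax and PEmax change as secondary. It describes pressure measurement by the tracker as something still to be developed.

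**The concern.** Progression of load largely defines what the trained arm receives. A study team reading section 3.0 would wait for device feedback. A team reading section 10.0 would have a clinician measure PEmax every week and reset the valve. A participant could be fully compliant under one text and a deviation under the other, yet fidelity is a primary analysis of this pilot.

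The choice also reaches a secondary outcome. PEmax depends on effort and can improve with repeated testing. If weekly tests are done in the trained arm only, some of the between-arm difference in PEmax change may be practice. The pilot is meant to inform a larger efficacy trial, so an unresolved progression rule would carry forward.

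**Working it through.** The plan states no number of load adjustments and no expected baseline PEmax, so there is no figure of its own to reproduce on this point. The confidence-interval precision in section 12.0 does not bear on it.

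**1. The two rules side by side.**

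| | Section 3.0 | Section 10.0 |
|---|---|---|
| Starting load | 70% of baseline PImax and PEmax | 75% of average baseline PEmax |
| Trigger | Device pressure feedback | Re-measured PEmax |
| Timing | Individual, "rather than simply increasing levels weekly" | Weekly |
| Actor | Text prompt to the participant | Research clinician |
| Means described | Pressure sensing to be added | Weekly reading; log of use times |

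**2. Readings the weekly rule needs.** Training lasts 6 weeks and week 1 uses the baseline setting. Resets for weeks 2 to 6 need 6 − 1 = 5 interim PEmax readings.

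**3. Readings the schedules provide.**
- Section 7.0, the Objective Measures table and the compensation paragraph: 0 between baseline and week 6. The compensation paragraph lists three visits where section 7.0 names two on site, but none of the three falls between baseline and week 6.
- End of the training-regimen text: 1, at week 3.
- Equipment: section 2.0 says these pressures are taken with a hand-held manometer, and the measures table names a calibrated meter. No section sends a pressure meter home. The device that section 10.0 offers to supply where needed is for peak flow, a different measurement.

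**4. Imbalance in testing if the weekly rule is followed.** Trained arm: 5 interim tests. Controls: 0 or 1. Excess: 5 − 1 = 4 or 5 − 0 = 5, taking the week-3 test as one of the trained arm's weekly tests.

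**5. Device limit.** The highest PEmax at which the device can deliver a given fraction is 20 divided by that fraction: 20/0.75 = 26.7 cm H2O and 20/0.70 = 28.6 cm H2O. The documents give no baseline PEmax, so the values below are assumed.

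| Assumed PEmax (cm H2O) | 75% target | 70% target | At the 20 cm H2O limit |
|---|---|---|---|
| 20 | 15.0 | 14.0 | 75% held until PEmax rises 33% |
| 25 | 18.8 | 17.5 | 75% held until PEmax rises 7% |
| 30 | 22.5 | 21.0 | at most 67% of PEmax |
| 60 | 45.0 | 42.0 | at most 33% |
| 100 | 75.0 | 70.0 | at most 20% |

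A valve already at its limit cannot be raised under either rule.

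**The case against.** The rules are not opposed in direction. Section 10.0 does not raise load automatically each week. It resets to measured strength and holds the load when PEmax is unchanged, and both rules raise load as strength improves. That is right, and the conflict is confined to trigger, timing, actor and starting percentage.

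A reader might infer that neither rule can run. The documents do not support that. Sections 3.0 and 12.0 plan pressure sensing, and section 3.0 names text prompts, which need no visit. Future tense in a protocol is a plan, not evidence of failure. What stands is that readiness is not stated, no reading that would trigger an increase is given, and section 10.0 describes only a log of use times.

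A reader might also infer that load will stay at its baseline setting for all six weeks and fall steadily as a share of current PEmax. That too goes beyond the text. The week-3 measurement allows one mid-course reset, and the size of any fall cannot be computed without a baseline PEmax, given the device limit and two different starting percentages.

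It can be said that a reading taken to set load is part of the intervention and need not appear in a data-collection table, and that a payment schedule is weak evidence of visits. Both are fair. The location statement in section 7.0 still leaves weekly pressure readings without a described place or instrument.

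Finally, pressure change is secondary and section 12.0 disclaims testing effectiveness. This lowers the severity but does not touch the fidelity problem.

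**Conclusion.** The contradiction holds and should be fixed. The protocol gives two escalation rules and two starting percentages. The weekly rule needs 5 interim readings against 0 or 1 scheduled. The feedback rule depends on a function still to be developed. The main consequence is that treatment fidelity has no single standard. The second is an excess of 4 to 5 PEmax tests in the trained arm if weekly testing is done. How much practice would add to PEmax cannot be sized from the documents.

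The device-limit thresholds of about 26.7 and 28.6 cm H2O follow from the stated range. They assume that the device described in section 3.0 is the one used in section 10.0. How many participants would exceed them is unknown.

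**What to change.** Amend sections 3.0 (both the rule and the device range), 7.0, 10.0 (measures table, training regimen, week-3 measurement and compensation) and 12.0 so that they state one escalation rule, one starting load and one measurement schedule that the device can deliver. Which rule and which load apply is a clinical decision for the investigators. Whatever they choose, the text should say what is measured, where, by whom and with which instrument.

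Record the date and valve setting of every adjustment as a fidelity item, and score fidelity against the rule chosen.

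Take outcome PImax and PEmax only at time points scheduled in both arms, including week 3 and week 14 if that schedule stands. If load-setting tests occur only in the trained arm, state the possible practice effect as a limitation on the PEmax comparison. Marking those readings as for load setting only would not remove it.

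The cost is mainly amendment wording and one log. If the weekly rule is kept, it means up to 15 × 5 = 75 measurement contacts, which section 10.0 already implies but section 7.0 does not accommodate. If the feedback rule is kept, the cost depends on how far the pressure sensing has been developed, which the documents do not say.

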## 1.0 Objectives / Specific Aims

Advances in mHealth technology and the ubiquity of smart phone access (~65% of adults in SC have a smart phone: ~75 % of youth older >12yrs) provide a viable approach for improved patient-provider interactions (8-17). Co-Investigator [name], collaborated with The Technology Applications Center for Healthful Lifestyles (TACHL) to develop the Smartphone Asthma Monitoring System (SAMS) with funding from a SCTR pilot award (UL TR000062) to transform post discharge phone call into a mobile technology platform. This monitor system will be repurposed and evaluated in an adult population with COPD, hence the renaming of **Smartphone Airway Monitoring System (SAMS 3.0)**. Numerous studies have demonstrated that exposures to environmental “cues” are associated with respiratory exacerbations, including locations (e.g., exposure to high allergen content –roaches in unkempt houses, etc.), situations (e.g. exercise, stress exposure), negative affective states and environmental context (e.g., time of day, after school outdoor activity). TACHL, in collaboration with various research teams funded by Verizon, Macey & Kellogg Foundations, Duke Endowment, and NIH, has successfully developed several smartphone-enabled biofunction monitoring, medical regimen adherence, and ecological momentary assessment (EMA) systems to assess an individual's emotional state, physical symptoms, functional status, and exposure to relevant environmental triggers (e.g., stress, physical exertion). The relay of self-reported information, biofunction data, and regimen adherence data in conjunction with GPS location tracking of use and associated pollen and pollution counts makes it possible to give a valuable report to a clinician to interact in real time with the patient. These interactions can be automated based on the guidelines (e.g., American Thoracic Society guidelines for COPD) and provider preference and/or live with the use of our evolving telemedicine infrastructure.

Further development of this mHealth solution (SAMS), in combination with a training regimen for the first time, will make this innovative approach to chronic respiratory disease more cost effective and sustainable over time (less personnel required). Preliminary work has been completed at MUSC to develop the SAM system and incorporate objective real-time measurement of medication use with self-report and Bluetooth enabled smart inhalers, EMA probe questions, and COPD follow up questions.

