### **Inclusion Criteria**

- 40 years of age or older; and
- Able to read and write English; and
- Diagnosed with COPD (PFT values: FEV1/FVC <0.7 and FEV1% predicted < 80% - within the past 6 months); or Dyspnea score of greater than "2" on the Modified Medical Research Council (MMRC) questionnaire.

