
will be continued without increase in the pressure threshold training level. All participants will be managed according to standard treatment protocols used within the MUSC Pulmonary Clinic. Detailed records will be kept pertaining to mortality and morbidity as well as use of inpatient and outpatient hospital facilities, medication use, frequency and duration of disease exacerbations, as well as general response to treatment. All dependent variables will be obtained, for all participants at baseline, mid-intervention (3 weeks post baseline), at intervention end (6 weeks) and 14 weeks (2 months) post baseline.

**Monitoring period:** As per our standard monitoring period with SAMS, participants will receive a daily EMA reminder text. Answering the EMA questions on a smartphone requires 30-45 seconds of time. Probes will occur to not interfere with typical sleep schedule or during school hours. EMA sessions will capture COPD symptoms and emotion/mood over the course of the day. If patients have not filled out an EMA in 3 days, a reminder text will be sent. EMA probe question responses will transfer to RedCap, as TACHL has done with other studies. Data will not be stored on the phone. The participants will be requested to perform video capture of training technique 1 time per week. A reminder will be sent during convenient waking hours if this has not been performed.

**Activity Tracking:** A Fitbit activity tracker will be provided to each participant and comprehensive instruction offered on its use. This activity tracking device is worn on the wrist and only removed for bathing or other activities involving water, as the devices are water-resistant but not waterproof.

**Quantitative and Qualitative Assessments:** Participants will complete quantitative and qualitative assessments of acceptability, feasibility, and performance of the SAM system including:

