One time per week of the study, the patients will be requested to perform video capture of training technique that will be reviewed by our PIs to determine beneficial elements of this video. If applicable, we will also compare return visits to the emergency department and hospital between previous enrollees in the last version of SAMS in a pediatric population. This "on the shelf data" of previous enrollees will be compared to the new enrollees with telehealth visits. 5) Qualitative Key Informant Interviews Qualitative data will be obtained via open-ended interview questions on the acceptability topics above. Interviews will be recorded for transcription and qualitative analyses will be applied using qualitative software program to determine themes in participant responses, which will prompt modifications to the SAMS program. Interviews may be performed over the phone if convenient for the family.

**Participant Compensation:** Participants will receive \$25 for screening, and \$25 at the initial enrollment visit for completion of the initial enrollment assessment and surveys (total of \$50 if enrolled). Additionally,

at the post study evaluation, they will receive up to \$75 for logging into app, wearing their Fitbit, and bringing back the study devices (e.g., Fitbit), completing EMA and surveys, and the brief key informant interview. Final visit compensation will be based on adherence to the study protocol including symptom data entry, EMA reports, telehealth visit, and final visit surveys/KIIs. Each day will be valued at \$2.50 and reimbursement will depend upon adherence to the study protocol including ensuring EMA symptom and training data is available for 5 days manually (for a total of \$12.50/week) for a total of \$75 over the six-week period. Tracking of reimbursement amount during the study will be delivered via the App in a compensation log. \$50 will be reimbursed for completing Visit 2 at Week 6, and another \$50 for completing the two-month follow-up visit. Total up to \$225 = \$75 (EMA and training data \$12.50/week x 6 weeks) + \$50 at Visit 1 + \$50 at Visit 2 + \$50 at Visit 3.

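### The conditional comparison of acute-care visits with earlier paediatric SAMS users cannot be interpreted; drop it and describe these visits by randomised arm

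*Combined protocol and SAP*

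**What the plan says.** The comparison is in Section 10.0, in the Assessments/Measures text below Figure 2. It opens conditionally, with an if-applicable clause, and concerns "return visits to the emergency department and hospital between previous enrollees in the last version of SAMS in a pediatric population". The following sentence carries no condition and says that the stored data "of previous enrollees will be compared to the new enrollees with telehealth visits". No criterion for applicability is given, nor the size of the earlier group, its observation window, a method, an adjustment, or which arm supplies the new enrollees.

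The current population is defined in Section 5.0, where the first inclusion criterion is "40 years of age or older; and". Section 1.0 describes the origin of the app as a project "to develop the Smartphone Asthma Monitoring System (SAMS" and continues: "This monitor system will be repurposed and evaluated in an adult population with COPD", under the name SAMS 3.0.

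On data within the trial, Section 10.0 states: "Detailed records will be kept pertaining to mortality and morbidity as well as use of inpatient and outpatient hospital facilities". Participants are randomised equally to standard of care (n=15) or standard of care plus training (n=15). The Statistical Analysis text in Section 12.0 uses emergency visits and hospitalisations only in relation to EMA responses. It contains neither the paediatric contrast nor a comparison by arm.

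**The concern.** An external control is informative only if the two groups would have had similar outcomes without the intervention, or could be made similar by adjustment. Children who used an earlier app and adults over 40 with COPD do not meet that condition. A difference in return visits could come from age, the underlying illness, the app version, the added training and telehealth, or the period. A real effect could equally be masked.

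Section 1.0 names fewer acute-care visits for COPD as the project's ultimate goal, so a figure on this outcome may attract attention whatever its standing in the plan. Meanwhile the trial has a concurrent randomised group and intends to record hospital use, yet states no summary of these visits by arm.

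**Working it through.** The documents give no sample size, event rate or precision for emergency or hospital visits, so there is no figure on this point to reproduce. The precision figures in Section 12.0 concern change scores and do not bear on it.

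**Step 1. The two groups side by side.**

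| Feature | Earlier enrollees | New enrollees | Basis |
|---|---|---|---|
| Age | Paediatric | 40 or older | Stated (Sections 10.0, 5.0) |
| App | Last version | SAMS 3.0 | Stated (Sections 10.0, 1.0) |
| Intervention content | Earlier SAMS | Telehealth visits, video capture and RMST logging added; training in one arm | Sections 1.0 and 10.0 |
| Disease | Probably asthma | COPD | Inferred from the app's former name |
| Period | Earlier, stored data | Concurrent | Implied; dates not given |

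Age alone decides the matter. Regression, matching and weighting all need some overlap in the covariate, and here there is none. Any adjusted estimate would be extrapolation.

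**Step 2. Illustration of what a baseline difference alone can do.** The visit rates and the historical group size are assumptions. Let n₁ adults (15 or 30) have visit probability pA and n₂ children (30 or 60) have pC, with no intervention effect. The chance of an apparently significant result is the sum, over all pairs (a, b) with two-sided Fisher p≤0.05, of Bin(a; n₁, pA) × Bin(b; n₂, pC). Ranges are across the four combinations of n₁ and n₂.

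| Children pC | Adults pA | Chance of p≤0.05 |
|---|---|---|
| 10% | 10% | 1% to 3% |
| 10% | 20% | 10% to 22% |
| 10% | 30% | 34% to 61% |
| 10% | 40% | 59% to 89% |

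**Step 3. What the randomised arms can offer.** For a common visit proportion p and n per arm, the 95% half-width for the difference is 1.96 × √(2p(1−p)/n).

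- n=15, p=0.10: 1.96 × √(0.18/15) = 0.215.
- n=15, p=0.40: 1.96 × √(0.48/15) = 0.351.
- With the 25 completers expected in Section 12.0, or 12.5 per arm on average: 0.235 and 0.384.

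The proportions are again assumed. Intervals this wide suit description, not testing.

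**Step 4. What the arms differ by.** The opening of Section 10.0 says that all 30 adults, 15 in each group, will have used SAMS for six weeks. Section 3.0 gives controls only the Fitbit, and the randomisation paragraph of Section 10.0 gives them the Fitbit and otherwise usual care. If both arms use SAMS, the randomised contrast says nothing about SAMS. If only one does, SAMS and training cannot be separated.

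**The case against.** The best defence is that this analysis carries little weight. It is conditional, is absent from the Statistical Analysis text even under the exploratory analyses, and serves no specific aim. Section 12.0 says the pilot is not meant to confirm or refute effectiveness. The interim-analysis section lists what will inform the larger trial, such as enrolment, retention, adherence, acceptability and user feedback; a historical contrast of acute-care visits is not on the list. References elsewhere to school hours, assent and the family suggest text carried over from paediatric work, although the documents do not say so. All of this stands and keeps the point small. It does not make the contrast interpretable, because no criterion for applicability is given and the second sentence is unconditional.

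A further objection is that the randomised arm is not a substitute. This is right. The historical contrast concerns SAMS versions and telehealth, whereas the randomised one concerns training added to standard of care. A reader might infer that the control arm answers the same question without bias, and the documents do not support that. The arms differ in a package whose content is described inconsistently. Randomisation removes baseline confounding, but about 5 of 30 participants are expected not to complete, hospitalisations are partly self-reported, and controls given only a Fitbit and usual care will know their arm.

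Finally, the lack of a table by arm is not in itself an error in a feasibility pilot. That also stands; the table is a cheap improvement.

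**Conclusion.** The point holds in limited form. If carried out, the paediatric comparison could not be attributed to SAMS, telehealth or training, and no adjustment would repair it. This conclusion needs only the non-overlap in age, which the documents state. The percentages in the illustration rest on assumed rates and group sizes; they show the mechanism, not an expected result.

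Two stronger readings are not supported. A reader might take the comparison as a firm or central analysis that will steer the larger trial, but it is conditional, and no sample size or decision rule depends on it. A reader might also take the disease difference as established. The plan calls the earlier users only paediatric, and asthma is a reasonable inference from the app's former name.

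**What to change.** - In Section 10.0, delete the two sentences on the paediatric comparison, or reword them so that the earlier data are background with no comparison made.
- In Section 12.0, add one descriptive table of emergency visits and hospitalisations by randomised arm: counts and rates with 95% confidence intervals, from baseline to 6 weeks and to 14 weeks where event dates allow. State that no hypothesis is tested, that the estimate concerns the randomised package, and that it is open to differential loss and self-report.
- Confirm that the utilisation records capture emergency visits and event dates. The sentence planning them names inpatient and outpatient use only and gives no observation window.
- Reconcile Section 3.0 with the opening and the randomisation paragraph of Section 10.0 on whether controls use SAMS.

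The cost is two sentences removed, one table added and a check of the data form. If the form already holds event type and date, no new data collection is needed.
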